## Intervention program

In May 2015, Seoul launched the TM alert system, called the dispatch-activated neighborhood access defibrillation and cardiopulmonary resuscitation program ("NAD-CPR" program) in 5 districts serving a population of 2.2 million (Gangdong-gu, Gangbuk-gu, Nowon-gu, Seocho-gu, and Jungnang-gu). The intervention consisted of three major components: registration of volunteers after CPR training, active installation and registration of a PAD, and dispatcher activation of registered volunteers for bystander CPR and defibrillation.

First, the CPR volunteer network was organized for those who agreed to register for the TM alert system after completing the CPR training courses provided in participating district health center. The CPR network was explained to the all trainee when CPR training was conducted and the trainees voluntarily registered themselves to the network after training. They were trained with a 1-hour CPR training course and received a certification card from the city mayor. The volunteers' telephone number, workplace address, and home address were collected and transferred to the dispatch center to integrate with the EMS call system. For quality control of the CPR trainee, the volunteer registration remained valid for 2 years, and after that it was automatically removed. If someone want to remain in the network after two years, they should be attend CPR renewal course and register again. The program started in

2013 as a pilot program and was implemented in 2014.

Second, the Seoul health authority expanded the installation of PADs. All PADs were registered in the National Emergency Medical Center by the EMS Act, and the PAD registry was developed and recorded for use. The active installation and registration of the PADs were guided by each district's health authorities at predesignated places by the EMS Act, such as public and commercial buildings, traffic stations, sports and cultural areas, and large-sized apartments. The city government provided half of the financial support for PADs, and the remainder were deployed by the private sector.

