### Study design

This was a non-randomized, pre- and post-intervention trial. Since the intervention program started in May 2015, the period from January 2013 to December 2014 was defined as the pre-intervention period, and the period from January 2015 to December 2016 was defined as the post-intervention period. The TM cases were defined as the cases for which an TM alert was sent. Other cases were defined as standard care cases (non-TM cases).

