### Study population

We enrolled all OHCA patients with a presumed cardiac etiology who were more than 15 years old and

who were treated by an EMS provider between January 2013 and December 2016 within the study area in Seoul. Those cases without an attempted resuscitation effort, cases that were witnessed by EMS providers or those that occurred at a nursing home or medical facility were excluded.

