### Statistical analysis

The demographics of the registered volunteers, registered PADs, and the number of TM alerts sent during the study period were compared for the study setting. A descriptive analysis was performed to determine the distribution of the categorical variables (counts and proportions) and continuous variables (medians and inter-quartile ranges). The chi-square test was performed for categorical variables, and the Wilcoxon rank-sum test was performed to compare continuous variables across the intervention periods.

Adjusted odds ratios (ORs) with 95% confidence intervals (CIs) for bystander CPR and defibrillation by TM versus non-TM were calculated using multivariable logistic regression analysis with adjustment for potential confounders. Adjustment for age, gender, and comorbidities were included as confounders in Model 1, and time factors (season, weekend, and time of the arrest) and characteristics of the arrest (witnessed, location of arrest) in addition to the confounders in Model 1 were added in Model 2.

Multivariable logistic regression analyses for outcomes (good CPC, survival to discharge, and PROSC) were used. Model 1 was adjusted for demographic factors (age, gender, and comorbidities); Model 2 was adjusted for the demographic factors from Model 1 as well as time factors related to the event (season, weekday, and daytime), Utstein factors (initial ECG, witness, and place), and EMS factors (RTI, STI, TTI, and prehospital airway); Model 3 was adjusted for the same confounders as Models 1 and 2 as well as factors related to advanced hospital care (PCI, TTM, and ECMO).

For the sensitivity analysis, a final multivariable logistic regression analysis was conducted for the subgroup population when the call occurred during the study time (TM sent time), from 6 AM to 10 PM. The confounders were same as the main analyses for each outcome. The main exposure was TM (cases who received TM alerts) versus non-TM (cases who did not receive TM alerts) for bystander CPR and defibrillation during the before- and after-intervention periods for outcomes (PROSC, survival to discharge, and good CPC).

All the statistical analyses were conducted using SAS software, version 9.4 (SAS Institute Inc., Cary, NC, USA). P values were based on a two-sided significance level of 0.05.

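### The alert comparison sets TM cases from May 2015 onward against other cases from January 2013, with no calendar term, so its odds ratio is confounded with calendar time

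*Combined protocol and SAP*

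**What the plan says.** The Intervention program section dates the start of alerts: "In May 2015, Seoul launched the TM alert system". The Study design section defines the two groups. On one side, "The TM cases were defined as the cases for which an TM alert was sent"; on the other, "Other cases were defined as standard care cases (non-TM cases". The Study population section takes in patients "who were treated by an EMS provider between January 2013 and December 2016 within the study area in Seoul".

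The Statistical analysis section then plans "Adjusted odds ratios (ORs) with 95% confidence intervals (CIs) for bystander CPR and defibrillation by TM versus non-TM were calculated" by multivariable logistic regression. Model 1 holds age, gender and comorbidities. Model 2 adds "time factors (season, weekend, and time of the arrest"), witness status and location of the arrest. Year, date and intervention period are not listed. The sensitivity analysis restricts the call to 6 AM to 10 PM and keeps the same confounders; it sets no date limit.

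The Intervention program section also describes two components that do not depend on an alert being sent. Volunteers were trained and registered, with a pilot in 2013 and implementation in 2014. In addition, "Second, the Seoul health authority expanded the installation of PADs".

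**The concern.** Read as written, the non-TM group combines two kinds of case: arrests from January 2013 to April 2015, when no alert could have been sent, and arrests after the launch that had no alert. TM cases are therefore later, on average, than the cases they are compared with. Season, weekend and time of day are cyclical, so January 2013 and January 2016 look the same to the model.

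A trained bystander or a nearby PAD can raise bystander CPR or defibrillation without any message. If these resources, or public behaviour generally, grew over 2013-2016, the TM coefficient picks up that growth. This is the plan's only comparison of alerted with unalerted cases, so an odds ratio above 1 is likely to be read as evidence that the message works. Defibrillation may be the more exposed outcome, since PAD expansion is a programme component in its own right.

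**Working it through.** The documents give no event rates, alert counts or sample size for this comparison, so there is no figure to reproduce. The window count comes from the documents; everything after it is illustrative.

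**Windows.** January 2013 to December 2016 is 48 months. January 2013 to April 2015 is 28 months (24 in the plan's pre-intervention period plus January to April 2015). May 2015 to December 2016 is 20 months. So 28/48 = 58% of the study period can supply only non-TM cases.

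**Assumptions.** Constant arrest rate; arrests spread evenly over 24 hours; after launch a constant share *s* of alert-hour arrests is alerted, with *s* from 20% to 70%; true alert odds ratio of 1.

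**Formulas.** Let *h* be the share of the analysed arrests that fall in alert hours: 16/24 = 2/3 in the all-hours analysis, 1 in the 6 AM to 10 PM analysis.
- TM fraction: f = (20/48) × h × s.
- Pre-launch share of the non-TM group: (28/48)/(1 − f).
- Mean date, in months from the start: all cases 24; TM cases 28 + 10 = 38; non-TM cases (24 − 38f)/(1 − f). The gap simplifies to 14/(1 − f) months.
- If background odds rise by a proportion g a year, the spurious odds ratio is about (1 + g) raised to the gap in years. Averaging a logistic trend (50% at mid-study) month by month gives the same values to two decimals.

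| Analysis | s | f | Pre-launch share of non-TM | Gap (years) | OR, 5%/yr | OR, 10%/yr | OR, 20%/yr |
|---|---|---|---|---|---|---|---|
| All hours | 20% | 0.056 | 62% | 1.235 | 1.06 | 1.12 | 1.25 |
| All hours | 70% | 0.194 | 72% | 1.448 | 1.07 | 1.15 | 1.30 |
| 6 AM to 10 PM | 20% | 0.083 | 64% | 1.273 | 1.06 | 1.13 | 1.26 |
| 6 AM to 10 PM | 70% | 0.292 | 82% | 1.647 | 1.08 | 1.17 | 1.35 |

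The clock-hour restriction does not help. It removes concurrent night-time controls, and the historical share rises.

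**In absolute rates.** If 10% to 50% of all post-launch cases are alerted and bystander CPR rises from 50% in 2013 to 60% in 2016, the spurious odds ratio is 1.18 to 1.22. With no rise it is 1.00.

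**Defibrillation.** With the same 10% to 50% alerted, a rise from 0.5% in 2013 to 1% in 2016 gives 1.29 to 1.37. With 1% at mid-study, odds rising 50% a year and the values of *s* in the table, monthly averaging gives about 1.5 to 1.8.

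**With the comparator limited to May 2015 onward.** If the alerted share is constant over those 20 months, the spurious odds ratio returns to 1.00 in every scenario. If the alerted share changes over those months, a calendar term is still needed within them.

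**The case against.** The strongest reply is that the bias is conditional. A reader might infer that the TM odds ratio does absorb a known rise in PADs and trained volunteers. The documents do not support that. The PAD expansion has no date, count or rate; no volunteer numbers are given, and registrations lapse after two years; no bystander CPR or defibrillation rate is stated for any year. At a 5% yearly rise in odds the distortion is only 1.06 to 1.08. This objection stands: the missing calendar term is certain from the text, while the direction and size of the bias are not.

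Nor are all the controls historical. Night-time arrests and other unalerted arrests after launch are in the non-TM group, so the confounding is partial.

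The plan never says that the TM exposure is meant to isolate the message, and volunteers and PADs belong to the same intervention. Their growth is a legitimate part of a before-after programme effect. It confounds only an odds ratio read as the effect of the alert. That reading is the natural one for an exposure defined by whether a message was sent, but it is an inference. So is the pooling: the Statistical analysis section does not name the analysis set, and pooling follows from the unrestricted group definition.

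Finally, a reader might conclude that a post-launch, alert-hour comparison should replace the main one. That goes too far. An alert follows the dispatcher's suspicion of arrest, so unalerted alert-hour cases after launch may be enriched for arrests that were not suspected. Those cases may have less bystander CPR for reasons unrelated to the alert, which would also push the odds ratio above 1.

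**Conclusion.** The concern holds in conditional form. The group definitions, the unequal windows (20 of 48 months against all 48) and the lack of any calendar term are in the text, and the sensitivity analysis does not repair them. TM status is therefore confounded with calendar time. The pooled odds ratio is free of this bias only if background bystander CPR and PAD use stayed flat over 2013-2016, which the plan neither states nor tests.

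Under the stated assumptions TM cases fall about 1.2 to 1.6 years later than non-TM cases. With bystander CPR near 50% and odds rising 5% to 20% a year, an alert with no effect would show an odds ratio of about 1.06 to 1.35. These figures show sensitivity; they do not estimate the bias in this study.

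The point is confined to the secondary exposure and the tertiary outcomes. The before-after models for neurological outcome, survival and prehospital ROSC are a separate matter.

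**What to change.** In the Statistical analysis section:

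1. State the analysis set for TM versus non-TM.
2. Add calendar time, from the date of arrest, to these models. Use year alongside the existing season term, or year-quarter in place of season. Year-quarter together with season may be collinear, depending on how season is coded. For defibrillation, use a coarser or linear term if events are sparse.
3. Report beside it a concurrent comparison limited to calls at 06:00-21:59 from the May 2015 launch to December 2016, also with a calendar term in case the alerted share changed over those months.
4. State that the pooled odds ratio without a calendar term will not be read as the effect of the alert.

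The cost is some wording, one covariate and one filter; the date of arrest and the time of the call are already collected. Confidence intervals will widen. The concurrent unalerted group may over-represent arrests that the dispatcher did not suspect, and the calendar-adjusted estimate also leans on those post-launch cases. Both results should be presented with that limitation stated.

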### Study population

We enrolled all OHCA patients with a presumed cardiac etiology who were more than 15 years old and

who were treated by an EMS provider between January 2013 and December 2016 within the study area in Seoul. Those cases without an attempted resuscitation effort, cases that were witnessed by EMS providers or those that occurred at a nursing home or medical facility were excluded.

#### Data collection and variables

We collected data from the Korean OHCA Registry including the ambulance run sheet, dispatch record, cardiac arrest in-depth registry, and medical records for outcomes from the Korea Centers for Disease Control and Prevention. We developed the TM alert system registry by linking the TM cases that had a message sent to the registered volunteers. We checked the OHCA registry to confirm whether or not the case was a real arrest. Such cases were excluded if they were not a cardiac arrest or death was confirmed at the scene and no transfer to the emergency department (ED) occurred.

The main exposure of interest was the intervention phase (before- and after-intervention periods), and the secondary exposure was TM sent from the TM alert system. Demographic factors that were collected included the following: date of arrest, time of the call (00:01-05:59, 06:00-11:59, 12:00-17:59, and 18:00-23:59), age, gender, and comorbidities (diabetes, hypertension, heart disease, and stroke). Community and EMS factors that were collected included the following: witness information, location of the arrest, bystander CPR, laypersons' use of a PAD, primary electrocardiogram (ECG) at the scene, EMS response time interval (RTI, from the time of the call to the time of EMS arrival at the scene), scene time interval (STI, from the time of arrival at the scene to the time of departure from the scene), transport time interval (TTI, from the time of departure from the scene to the time of EMS arrival at the hospital), prehospital airway management by an EMS provider (endotracheal intubation, supraglottic airway device, or bag valve mask). Hospital factors included the emergency department (ED) level (regional level 1 ED, local level 2 ED, local level 3 ED) and post-resuscitation care, such as percutaneous coronary intervention (PCI), targeted temperature management (TTM), and extracorporeal membrane oxygenation (ECMO).

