Third, according to the DA-CPR protocol, the dispatcher asked two key questions regarding altered mental status and abnormal breathing. When a suspected arrest occurred, to issue an alert about an OHCA event, the dispatchers pushed a button to send a short text message containing the location of the cardiac arrest and the location of nearest available PAD to registered all volunteers within one geographic town according to a time window. This time window address-matched volunteers to their workplace or home address during the intervals from 6 AM to 22PM. The protocol for the TM alert service was not applied to all OHCA, especially in cases which occurred during the time interval from 00:00-05:59 and 22:00-23:59, because the night was regarded as an ineffective time to alert volunteers due to being too late.

The dispatchers, EMS crew, registered CPR volunteers, and medical record reviewers who were employed to review the hospital outcomes by the Korea CDC were blinded to the study intervention.

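### The 18:00-23:59 time-of-call class crosses the 22:00 alert cut-off, so adjusting for it would not fully control for alert eligibility in the TM versus non-TM comparison

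*Combined protocol and SAP*

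**What the plan says.** Intervention program: volunteers were matched to an address for alerting "during the intervals from 6 AM to 22PM", and the alert service was not applied "during the time interval from 00:00-05:59 and 22:00-23:59".

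Study design: a TM case is one for which an alert was sent. "Other cases were defined as standard care cases (non-TM cases". A call at 23:00, when no alert could go out, is therefore a non-TM case.

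Data collection and variables: the call-time variable is "time of the call (00:01-05:59, 06:00-11:59, 12:00-17:59, and 18:00-23:59". The same section ranks the exposures: "The main exposure of interest was the intervention phase (before- and after-intervention periods), and the secondary exposure was TM sent from the TM alert system".

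Statistical analysis: odds ratios "for bystander CPR and defibrillation by TM versus non-TM were calculated using multivariable logistic regression analysis". Model 1 has no time term. Model 2 adds "time factors (season, weekend, and time of the arrest", together with witnessed status and location of arrest. The coding of time of arrest is not given there. A sensitivity analysis repeats TM versus non-TM, with the same confounders, on calls from 06:00 to 22:00 only.

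**The concern.** A call's clock time decides whether it could be a TM case at all. A time covariate controls for that only if each of its classes lies wholly inside or wholly outside the alert window. Three classes do: 00:01-05:59 is all ineligible, and 06:00-11:59 and 12:00-17:59 are all eligible. The 18:00-23:59 class is not. Every TM case in it comes from before 22:00, while its non-TM cases include every arrest from 22:00 onward.

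If bystander CPR or defibrillation is less frequent after 22:00 than earlier in the evening, part of that difference is credited to the alert. If it is more frequent, the bias runs the other way. The documents give no rates by hour, but the protocol's own reason for stopping alerts at night is that volunteers would be hard to mobilise, so a change in bystander behaviour around then is plausible.

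At stake is the TM odds ratio for bystander CPR and defibrillation, the outcomes closest to how the alert is meant to work. As a side point, 00:00 itself falls in no class.

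**Working it through.** The documents state no rates, event counts or effect size for this contrast, so there is no planned figure to reproduce.

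**1. Interval check (from the documents)**

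| Class as collected | Alert-eligible hours | Ineligible hours |
|---|---|---|
| 00:01-05:59 | 0 | 6 |
| 06:00-11:59 | 6 | 0 |
| 12:00-17:59 | 6 | 0 |
| 18:00-23:59 | 4 | 2 |
| Total | 16 | 8 |

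Six of the 8 ineligible hours are isolated in their own class. Two are not.

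**2. Assumptions for size (none from the documents)**

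No true alert effect; arrests even by hour; a share q = 0.40 of post-period alert-hour arrests alerted; bystander CPR 55% in alert hours and 50%, 45% or 40% outside them; pre- and post-periods of equal size. The plan does not say whether pre-period cases enter the non-TM group, so both versions are shown.

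**3. Odds ratio inside the 18:00-23:59 class**

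Non-TM weights for eligible and ineligible hours:

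- Post-period only: 4(1 - 0.4) = 2.4 and 2.
- With pre-period: 4 + 2.4 = 6.4 and 4.

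For a 40% night rate, post-period only, the non-TM mean is (2.4 × 0.55 + 2 × 0.40)/4.4 = 0.4818. The odds ratio is (0.55/0.45)/(0.4818/0.5182) = 1.31. The three night rates give 1.10, 1.20 and 1.31 post-period, and 1.08, 1.17 and 1.26 with pre-period cases. No planned analysis reports these within-class values.

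**4. The odds ratio the model would report**

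Model 2 gives one TM odds ratio across classes. The two daytime classes contribute a log odds ratio of 0, and the 00:01-05:59 class has no TM cases and contributes nothing. Taking each class's weight as approximately n(TM) × n(non-TM)/n(total):

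- Post-period only: each daytime class 2.4 × 3.6/6 = 1.44; evening class 1.6 × 4.4/6 = 1.173. Evening share = 1.173/(2 × 1.44 + 1.173) = 0.289.
- With pre-period: each daytime class 2.4 × 9.6/12 = 1.92; evening class 1.6 × 10.4/12 = 1.387. Evening share = 1.387/(2 × 1.92 + 1.387) = 0.265.

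For a 40% night rate: exp(0.289 × ln 1.314) = 1.08 post-period, and exp(0.265 × ln 1.260) = 1.06 with pre-period cases. A logistic regression on the expected counts agrees:

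| Bystander CPR outside alert hours | Four classes, post-period non-TM | Four classes, with pre-period | Split at 22:00, or restricted to 06:00-22:00 |
|---|---|---|---|
| 50% | 1.03 | 1.02 | 1.00 |
| 45% | 1.05 | 1.04 | 1.00 |
| 40% | 1.08 | 1.06 | 1.00 |

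With no time term, as in Model 1, the same assumptions give 1.10, 1.20 and 1.31 post-period.

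**5. Wider assumptions**

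The second set takes bystander CPR of 60% against 55%, 50% or 40%; defibrillation of 5% against 2%; 15%, 30% or 60% of eligible calls alerted; 25% or 33% of the last class falling after 22:00; and uneven class sizes (7:12:10:11). The four-class model then gives 1.02 to 1.16 under no effect, against 1.06 to 1.47 with no time term. With a true odds ratio of 1.50 it gives 1.53 to 1.75. Splitting at 22:00 or restricting to alert hours returns 1.00 and 1.50.

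**The case against.** The strongest reply is that the plan already contains the remedy. The 06:00-22:00 sensitivity analysis uses the same exposure, bystander outcomes and confounders, and removes every ineligible hour. That is correct, and it limits the consequence. It does not correct the all-hours analysis, which is the main one for this contrast, and the plan does not say which result stands if the two differ.

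Second, the coding of time of arrest in Model 2 is not stated, so the four classes may not be what enters the model. This stands, and the point is conditional on it. These are, however, the only time-of-day classes the documents define.

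Third, Model 2 already adjusts for witnessed status and location, which may explain part of any evening-to-night difference. This also stands. The illustration ignores both, so its assumed gap should be read as what remains after them.

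A reader might infer more than the documents support:

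- That the time variable cannot control for eligibility at all. Three of the four classes align with the alert window, and under the stated assumptions adjustment takes a spurious 1.31 down to 1.08.
- That the reported TM odds ratio would be inflated to as much as 1.31 despite the adjustment. That figure applies inside one class; the pooled model gives about 1.08.
- That the primary result is at risk, or that every model needs recoding. The primary endpoint is analysed by before/after period, not by TM status. TM is the secondary exposure, and bystander CPR and defibrillation are tertiary outcomes.

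The missing 00:00 is one minute a day and probably a labelling slip.

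**Conclusion.** The point holds in a limited form. The 18:00-23:59 class mixes eligible and ineligible hours, so if it is the class used in Model 2, adjustment for alert eligibility in the all-hours TM versus non-TM analysis is incomplete by 2 of 8 hours. Under the main assumptions the resulting bias in a null odds ratio is between 1.02 and 1.08; the wider set reaches 1.16. All these sizes rest on assumed bystander rates and alert shares, and the bias vanishes if bystander rates do not change after 22:00. It is confined to tertiary outcomes and is absent from the 06:00-22:00 analysis. It is worth correcting because the correction is simple and the TM odds ratio bears directly on how the alert is meant to work.

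**What to change.** In the TM versus non-TM models, state that time of arrest enters as call time in four classes: 22:00-05:59, 06:00-11:59, 12:00-17:59 and 18:00-21:59. No class then crosses an alert boundary, and 00:00 is covered. The recode uses a call time already collected and the same number of classes, so it has no material cost.

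Optionally, present the planned 06:00-22:00 restriction as the main TM versus non-TM contrast and the all-hours version as supporting. This would also protect Model 1, which has no time term and so gains nothing from the recode. It needs no new analysis. The ineligible calls it drops contain no TM cases, so they carry no direct information on the contrast. Neither change addresses other differences between alerted and non-alerted calls within alert hours.
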